3.2 Analysis Populations

3.2.1 Intent-to-Treat Population and Modified Intent-to-Treat Population

The Intent-to-Treat (ITT) Population will include all patients who are randomized in the study and receive at least 1 dose of study drug. The ITT population is defined as identical to the Safety Population.

The modified intent-to-treat (mITT) population includes all patients who are randomized in the study, received at least 2 weeks of study drug, and have valid lipid measurement at Week 2 or later visits. The mITT Population will be used for all efficacy analyses.

3.2.2 Per Protocol Population

The Per Protocol Population will include all mITT patients who finish the Week 12 visit with valid LDL-C measurements, have sufficient treatment compliance, and do not have any major protocol deviations. The following will be evaluated for major deviations prior to unblinding of the treatment allocation:

- Patients who violated eligibility criteria;
- Patients who did not complete the study;
- Patients who were <80% compliant with study drug;
- Patients who took prohibited concomitant medications;
- Patients who were unblinded; and
- Patients who had other substantial protocol deviations that may impact the efficacy assessment.

The Per Protocol Population will be used to assess robustness of the primary efficacy analysis results.

3.2.3 Safety Population

The Safety Population will include all patients who are randomized in the study and receive at least 1 dose of study drug and will be used for all safety analyses.

3.3 Patient Disposition

The reason given for each screen failure will be summarized and listed. Patient disposition will be provided for all randomized patients. The number and percentage of patients in each of the following disposition categories will be presented:

- Patients who are randomized,
- Patients who start study drug,
- Patients who complete the 12-week study drug,
- Patients who complete the study (Week 12), and
- Patients who withdraw from the study.

For randomized patients who withdraw from the study, the primary reason for the withdrawal will be listed and summarized.

The number of patients included in each analysis population will be summarized.

3.4 Demographics and Baseline Characteristics

Demographics (age, sex, race, and ethnicity), body weight, height, and body mass index (BMI) will be summarized by randomized treatment using descriptive statistics for the randomized patients based on the Safety Population. Age group (<65 years, or \geq 65 years), BMI category (<25 kg/m², 25-30 kg/m², or >30 kg/m²), statin category (Atorva 80 mg, Rosuva 20/40 mg, or No/Low Dose Statin), statin use (Atorvastatin, Rosuvastatin, Pravastatin, or None), Ezetimibe Use (Yes, or No), and undergoing PCSK9 inhibitor treatment (Yes, or No) will also be summarized.

Medical history will be coded using the Medical Dictionary for Regulatory Activities (MedDRA). The number and percentage of patients with medical history will be summarized by their MedDRA preferred term within system organ class and by treatment.

3.5 Prior/Concomitant Medications

The use of any prior medication and concomitant medication will be listed for the Safety Population with an indication of whether the medication was prior or concomitant during the study.

Medications will be coded using the most recent version of World Health Organization (WHO) Drug Dictionary. The number and percentage of patients taking each concomitant medication will be summarized by preferred term within Anatomical Therapeutic Chemical classification and by treatment group for the Safety Population. A concomitant medication is defined as any medication taken on or after the first dose day of study medication.

3.6 Study Medication Exposure and Compliance

Days of exposure to study medication will be summarized by treatment group for the Safety Population using descriptive statistics. Exposure in days is defined as the date of last dose of study drug minus the date of first dose of study drug plus 1. In addition, a contingency table will be provided to display the number and percentage of patients with exposure in the following categories:

- 1 to \leq 2 weeks (1-14 days),
- >2 to \leq 4 weeks (15-28 days),
- >4 to \leq 8 weeks (29-56 days),
- >8 to \leq 12 weeks (57-84 days), and
- >12 weeks (85 days or more).

Compliance between Weeks 4 and 12 will be calculated based on the total actual number of capsules taken as compared to the total expected number of capsules taken (2 per day). Percent compliance with the study medication will be summarized by treatment group for the Safety Population using descriptive statistics. Additionally the number and percentage of patients within each treatment group with overall compliance in the following categories: <80%, 80% to 120%, and >120%, will be provided. Overall compliance will not be calculated.

Patients randomized to active study drug will be treated as follows: On the morning of Day 1, patients will receive MGL-3196 100 mg. At the Week 2 visit, patients will be administered one dose of MGL-3196 100 mg, and a 4 hour postdose MGL-3196 PK assessment will be made while patients are fasting. Patients will receive MGL-3196 60 mg between the Week 2

and Week 4 visits. At the Week 4 visit, patients will either continue to receive MGL-3196 60 mg or be placed back on 100 mg depending on their Week 2 MGL-3196 level at 4 hours postdose. (Patients with Week 2 postdose MGL-3196 blood levels < 1,500 ng/mL will be placed on MGL-3196 100 mg while patients with MGL-3196 blood levels \geq 1,500 ng/mL will continue to receive 60 mg.) The duration of each dose level will be summarized and number/percentage of patients taking each dose at each visit will be tabulated.

3.7 Analysis of Efficacy

3.7.1 Descriptive Statistics

All available raw and derived data will be listed for the randomized patients. Descriptive statistics for baseline, change from baseline or percent change from baseline to each post-baseline visit will be presented by treatment group for each efficacy measurement for the mITT Population.

3.7.2 Primary Efficacy Analyses of LDL-C

The primary efficacy variable will be the percent change in LDL-C from baseline to Week 12. Summary statistics (number of patients, mean, standard deviation, median, minimum, and maximum) at all visits and change and percent change from baseline will be provided.

The primary efficacy variable, the percent change in LDL-C from baseline to Week 12, will be analyzed using an analysis of variance (ANOVA) model with treatment (MGL-3196 or placebo) as a factor based on the mITT population. For any patients in the mITT Population with a missing primary efficacy variable, the last post-baseline observation carried forward (LOCF) method will be used. The least-squares mean, 95% confidence interval, and p-value will be provided for the comparison of MGL-3196 versus placebo.

Sample SAS® code is provided below:

```
*****

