10.2 Statistical Methods

10.2.1 Analysis of Efficacy

10.2.1.1 Primary efficacy analysis

The primary efficacy variable will be the change in LDL-C from baseline to Week 12. Summary statistics (number of patients, mean, standard deviation, median, minimum, and maximum) at all visits and change from baseline will be provided. The primary efficacy analysis will be analyzed with an analysis of covariance (ANCOVA) model with treatment as a factor and baseline LDL-C as a covariate. Determinations for the 100 (and 60) mg groups will be based on all 12 weeks of the study, including the first two weeks (Week 0-2) in which all patients were on 100 mg and the second two weeks (Week 2-4) when all patients down-titrated to 60 mg. The assigned group (60 or 100 mg) will be based on the dose at Week 4 to Week 12. For any patients in the ITT Population with a missing primary efficacy parameter, the last observation carried forward method will be used. The multiplicity (MGL-3196 100 mg versus placebo and MGL-3196 60 mg versus placebo) will be controlled by Dunnett's Test. The primary efficacy analysis will be performed based on the ITT Population and repeated based on the Per Protocol Population.

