10.2.1.2 Secondary efficacy analysis

For the continuous secondary efficacy variables, the same ANCOVA model will be used. Normality will be tested for the model residuals. For certain efficacy variables, logarithm transformation may be performed prior to fitting the ANCOVA model. For the categorical secondary efficacy variables, Fisher's exact test will be used to compare the odds ratio between MGL-3196 doses versus placebo.

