2.3 Study Endpoints

2.3.1 Efficacy Variables

The primary efficacy parameter is mean percent change from baseline in LDL-C.

The secondary efficacy parameters include the following:

- Mean percent change from baseline in non-HDL-C, ApoB, TC/HDL-C ratio, triglycerides, lipoprotein(a) (Lp(a)), ApoB/ApoA1 ratio, Apolipoprotein CIII (ApoCIII), and lipoprotein particle assessment;
- Absolute change from baseline in LDL-C;
- Mean percent change from baseline in LDL-C for all patients on study drug (60-100 mg); and
- Mean percent change from baseline in LDL-C according to MGL-3196 exposure.

The exploratory efficacy parameters include the following:

- [REDACTED]
- [REDACTED]
- [REDACTED]
- [REDACTED]

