** PCHG = Percent change in LDL-C from Baseline to Week 12      **
** TRT = Treatment group where 0 = placebo, 1= MGL-3196           **
*****
PROC GLM;
  CLASS TRT;
  MODEL PCHG = TRT;
  LSMEANS TRT / e pdiff=control("0") cl;
RUN;
```

In addition to the percent change from baseline to Week 12 in LDL-C, the change in LDL-C from baseline to Week 12 will be analyzed using an analysis of covariance (ANCOVA) model with treatment as a factor and the baseline value as a covariate. For any patients in the mITT Population with a missing primary efficacy variable, the LOCF method will also be used.

Sample SAS® code is provided below:

```
*****

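### Low-cost improvement: the SAP's primary percent-change analysis of LDL-C omits baseline without a reason, while its absolute-change analysis adjusts for it

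*SAP*

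**What the plan says.** **SAP 3.7.2.** The primary variable is percent change in LDL-C at Week 12, which the section says "will be analyzed using an analysis of variance (ANOVA) model with treatment (MGL-3196 or placebo) as a factor based on the mITT population". The sample code agrees: "MODEL PCHG = TRT", with no baseline term. The section then adds a second analysis: "the change in LDL-C from baseline to Week 12 will be analyzed using an analysis of covariance (ANCOVA) model", with the baseline value as covariate. SAP 2.3.1 lists that second variable, "Absolute change from baseline in LDL-C", as a secondary parameter.

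**Protocol 10.2.1.1.** The primary model is an "analysis of covariance (ANCOVA) model with treatment as a factor and baseline LDL-C as a covariate". The same paragraph words the variable as follows: "The primary efficacy variable will be the change in LDL-C from baseline to Week 12". Yet the primary objective (2.1), the efficacy parameters (7) and the sample-size section (10.2.4) all refer to percent change.

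**Secondary endpoints.** Protocol 10.2.1.2 says: "For the continuous secondary efficacy variables, the same ANCOVA model will be used". SAP 3.7.5 likewise sends continuous endpoints to the ANCOVA of the primary analysis. SAP 2.3.1 defines most of these endpoints as percent changes: "Mean percent change from baseline in non-HDL-C, ApoB, TC/HDL-C ratio, triglycerides" and others.

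**The concern.** The one estimate that will be read as the trial result is the one not adjusted for baseline LDL-C. Baseline is used in the absolute-change ANCOVA, the multiple imputation, the baseline subgroups and the target-attainment logistic models. No specified model adjusts the percent-change estimate for it, and the sensitivity MMRM lists no baseline term either.

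Three things are at stake, all modest:

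- some precision, if percent change is correlated with baseline;
- protection of the headline figure against a chance baseline imbalance between 70 and 35 patients;
- a traceable link to the protocol, whose primary model includes baseline. SAP section 1 promises to document only deviations from the SAP itself, so nothing obliges anyone to explain this choice.

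A related gap is in SAP 3.7.5. The primary variable has an ANOVA, and the only ANCOVA in 3.7.2 has absolute change as its response. A programmer told to use the primary ANCOVA for endpoints defined as percent changes could reasonably fit either response.

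**Working it through.** **Inputs.** Difference 20 points, SD 20, 27 completers per group, alpha 0.025, 90% power, and 70 v 35 randomized: protocol 10.2.4 and SAP 4. The within-group correlation r of percent change with baseline LDL-C is in neither document. It is assumed here, from 0 to 0.5 in absolute value, with 0.355 as an intermediate point. SAP 3.7.4 notes high variation between screening and baseline LDL-C, but this cannot fix r: statin dosing moves to the evening around screening, so part of that variation may be a real shift.

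**The plan's own figure.** Noncentral-t power for a two-sample t-test, two-sided alpha 0.025, is 89.8% at 26 per group and 91.0% at 27. The stated 27 per group for 90% power reproduces.

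**ANOVA, pooled MGL-3196 v placebo, 70 v 35.** SE = 20 × √(1/70 + 1/35) = 20 × 0.2070 = 4.140. With t(103) = 1.983, the 95% half-width is 8.21 points.

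**ANCOVA, N = 105.** SE = 20 × √(1 − r²) × √[(1/70 + 1/35) × (1 + 1/(N − 4))]. The factor 1 + 1/101 is the average cost of estimating the slope. The reference distribution is t(102).

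**Imbalance.** One standard error of the baseline mean difference is √(1/70 + 1/35) = 0.207 SD. It shifts the unadjusted estimate by r × 20 × 0.207 points.

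| r (absolute, assumed) | ANCOVA SE | 95% half-width | v ANOVA 8.21 | Shift in ANOVA estimate, 1-SE imbalance |
|---|---|---|---|---|
| 0 | 4.161 | 8.25 | +0.5% | 0 |
| 0.10 | 4.140 | 8.21 | 0% (break-even) | 0.41 |
| 0.20 | 4.077 | 8.09 | −1.5% | 0.83 |
| 0.355 | 3.890 | 7.72 | −6.0% | 1.47 |
| 0.50 | 3.603 | 7.15 | −13.0% | 2.07 |

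**With 54 v 27 completers** (assumed: the planned 27 at 2:1), the half-width is 9.38 by ANOVA. By ANCOVA it is 9.45 at r = 0, 9.38 at 0.115 (break-even) and 8.83 at 0.355.

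**Power, two-sided 0.05** (assumed for the single pooled comparison):

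- 20 points, 70 v 35: 99.76% by ANOVA; 99.75% (r = 0) to 99.91% (r = 0.355) by ANCOVA.
- 20 points, 54 v 27: 98.7% by ANOVA; 98.6% to 99.4% by ANCOVA over the same range.
- 10 points (assumed), 70 v 35: 66.7% by ANOVA; 66.3% (r = 0) to 72.1% (r = 0.355) by ANCOVA.

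**Type I error.** In 20,000 simulated null trials at each of six values of r from 0 to 0.355, both models rejected in 4.6% to 5.3%.

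**The case against.** The strongest reply is that this is a preference. The ANOVA is valid, percent change is already scaled to baseline, and ANCOVA narrows the interval only if r exceeds about 0.10, a value that nobody can take from the documents. All of that stands, and it is why the point is minor. It does not favour the ANOVA, though: the possible loss is about 0.5% of the half-width, and the possible gain is several times that.

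The second reply is that the SAP did not drop the protocol's model. Protocol 10.2.1.1 literally names change in LDL-C, and the SAP runs exactly that ANCOVA alongside the ANOVA. This is a fair reading, so the ANOVA cannot be called a clear departure. But the protocol's objective, efficacy parameters and sample size all concern percent change, and its ANCOVA is extended to secondary variables defined as percent changes. The protocol is ambiguous, and the SAP resolves the ambiguity without saying so.

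Third, the imbalance shifts are small against a half-width of about 8 points and a planned effect of 20. That also stands; a changed conclusion at the planned effect is unlikely. Nor would adding baseline by itself align the SAP with the protocol, because the SAP's primary analysis also differs in its population and in pooling the two dose groups.

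Finally, SAP 3.7.5 does settle the scale for triglycerides if they are log-transformed: log values, back-transformed to percent change. The response remains open for the other endpoints.

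**Conclusion.** The point holds, as a minor, low-cost improvement. The SAP text and code both give the primary percent-change variable a treatment-only model, no reason is stated, and no specified model adjusts that estimate for baseline LDL-C. Validity, type I error and power at the planned effect are not in question.

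At 70 v 35 and SD 20, adjustment changes the 95% half-width by between +0.5% (r = 0) and −6.0% (r = 0.355), or −13.0% if r reached 0.50. It also removes a shift of roughly 0.4 to 1.5 points, for r from 0.10 to 0.355, under a one-standard-error baseline imbalance. These sizes rest on an assumed r; the textual findings do not. The unsettled response variable in SAP 3.7.5 is a separate wording gap that does not depend on r.

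**What to change.** - In SAP 3.7.2, make the primary model `PCHG = TRT BASE` and keep the unadjusted ANOVA as a sensitivity analysis.
- If the ANOVA is to stay primary, state why, and how it relates to the protocol's ANCOVA, before unblinding.
- In SAP 3.7.5, name the response for each continuous secondary endpoint. A workable default is percent change with treatment and the endpoint's own baseline value. For variables that are log-transformed, use change in log value with log baseline as covariate, back-transformed to percent change as the section already plans.
- Optionally, add baseline LDL-C to the sensitivity MMRM.

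**Cost.** For the primary model, one term in the code and one degree of freedom (SE about 0.5% larger at 70 v 35 if r = 0). The 3.7.5 change takes somewhat more drafting, because each endpoint needs its response stated. No new data are needed, since baseline lipids are already collected.

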5 STUDY TREATMENTS

5.1 Treatment Groups

Patients who qualify for study inclusion will initially be randomized (2:1) to receive once-daily MGL-3196 100 mg or once-daily matching placebo given orally in the morning. All patients randomized to MGL-3196 will initially receive 100 mg QD through the week 2 visit, then 60 mg QD until the week 4 visit. At the week 4 visit, patients receiving MGL-3196 will be placed back on 100 mg if their week 2 MGL-3196 level 4 h postdose is < 1,500 ng/mL and described as the “100 mg group”; if the level of MGL-3196 \geq 1500 ng/ml they will continue to receive 60 mg QD for weeks 4-12 and will be described as the “60 mg group”. In summary, the assigned treatment groups are as follows:

- Placebo
- “100 mg group”: patients administered MGL-3196 100 mg for weeks 1-2, 60mg between week 2-4 visits, and 100 mg for weeks 4-12
- “60 mg group”: patients administered MGL-3196 100 mg for weeks 1-2 and 60 mg for weeks 2-12

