2. STUDY OBJECTIVES AND STUDY DESIGN

2.1 Study Objectives

2.1.1 Primary Objective

The primary objective of this study is to determine the effect of each of two separate treatment groups (the “100 mg group” and the “60 mg group”) of once-daily oral dose of MGL-3196 and matching placebo on the percent change from baseline in low-density lipoprotein cholesterol (LDL-C) in patients with heterozygous familial hypercholesterolemia (HeFH).

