** CHG = Change in LDL-C from Baseline to Week 12      **
** TRT = Treatment group where 0 = placebo, 1= MGL-3196           **
** BASE = Baseline LDL-C                                     **
*****
PROC GLM;
```

```
CLASS TRT;  
MODEL CHG = TRT BASE;  
LSMEANS TRT / e pdiff=control("0") cl;  
RUN;
```

The same analysis models for Week 12 LDL-C are also used to analyse the percent change and change in LDL-C from baseline at Week 2 and Week 4 LOCF.

The primary efficacy analysis will be performed based on the Per Protocol Population to evaluate the robustness of the primary efficacy analysis.

Other imputation method for missing values of Week 12 LDL-C will be evaluated, including multiple imputation and Mixed Model for Repeated Measurements (MMRM) method based on the mITT population. The multiple imputation method will use statin group (80 mg Atorvastatin, 20/40 mg Rosuvastatin, or No/Low Dose Statin), baseline and all the post-baseline valid LDL-C values as references for the imputation with the monotone missingness assumption. The MMRM method will include treatment and visit as factors, and treatment by visit interaction.

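### Primary LOCF lets an early point of the dose titration stand in for Week 12 LDL-C, and the MMRM that could replace it is planned without baseline LDL-C

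*SAP*

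**What the plan says.** **Missing data.** Protocol 10.2.1.1 says that for a missing primary parameter "the last observation carried forward method will be used". SAP 3.7.2 keeps this for the mITT population: "the last post-baseline observation carried forward (LOCF) method will be used". Under SAP 3.2.1, two weeks of drug and one valid lipid value at Week 2 or later are enough to enter the mITT. SAP 3.1 treats lipids taken two days or more after the last dose as not valid. A single Week 2 or Week 4 value can therefore become a patient's Week 12 result.

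**Dose schedule.** Protocol 5.1: "All patients randomized to MGL-3196 will initially receive 100 mg QD through the week 2 visit, then 60 mg QD until the week 4 visit". The 100 mg group then has "60mg between week 2-4 visits, and 100 mg for weeks 4-12", and the 60 mg group stays on 60 mg. Placebo patients stay on placebo throughout.

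**Model and contrast.** The SAP primary analysis is an "analysis of variance (ANOVA) model with treatment (MGL-3196 or placebo) as a factor based on the mITT population", so the active arm is pooled. The protocol's primary analysis is an "analysis of covariance (ANCOVA) model with treatment as a factor and baseline LDL-C as a covariate", with each dose group compared with placebo. The SAP's stated objective is still to "determine the effect of each of two separate treatment groups (the “100 mg group” and the “60 mg group" have on LDL-C. The SAP's by-dose result is the final-dose repeat in 3.7.3. A further ANCOVA in 3.7.2, on absolute change, does include baseline.

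**Alternatives already planned (SAP 3.7.2).** Multiple imputation uses statin group, baseline and all valid post-baseline LDL-C values. For the other alternative: "The MMRM method will include treatment and visit as factors, and treatment by visit interaction". No baseline term and no covariance structure are given. SAP 3.7.5 lists the same MMRM terms for other endpoints.

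**The concern.** LOCF assumes that LDL-C would have stayed at its last value. Here the design changes the dose in one arm during the very period that LOCF bridges, so the assumption conflicts with the treatment plan for some active patients and for no placebo patients. For the pooled contrast, the consequence is that a point partway through the titration replaces the Week 12 response. For the by-dose comparisons, some carried values come from a dose other than the one that labels the group.

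At stake is the size of the reported effect, which a Phase 2 study hands on to later planning. The direction of any error depends on when patients leave and on how LDL-C moves over time, and neither is known in advance. The SAP already contains a model that uses the same visits without holding values constant. However, that model has only a sensitivity role and leaves out a baseline value that the protocol's own primary model requires.

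**Working it through.** **1. The plan's own figure.** Protocol 10.2.4 and SAP section 4 give a difference of 20, SD 20, alpha 0.025 and 27 completers per group for 90% power. A two-sided two-sample t-test (noncentral t; two-sidedness assumed) gives 91.0% at 27 per group and 89.8% at 26. The figure is reproduced. It does not depend on the choice between LOCF and MMRM.

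**2. Which carried values come from a different dose** (Protocol 5.1, SAP 2.2)

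| Last valid visit | Active dose at that visit | 100 mg group | 60 mg group |
|---|---|---|---|
| Week 2 | 100 mg | same | differs |
| Week 4 | 60 mg | differs | same |
| Week 8 | the Week 4–12 dose | same* | same* |

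*Unless down-titrated for TSH. Placebo never differs.

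**3. Bias under assumed trajectories.** Let E be the difference from placebo at each visit and d the share imputed. Assume d is equal in both arms and last visits are spread evenly over Weeks 2, 4 and 8.

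Expected LOCF effect = (1 − d) × E12 + d × (E2 + E4 + E8)/3

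Values used for d are 0.10 and 0.23. The upper value is 1 − 27/35 = 22.9%, the room the sample size leaves for dropout; the documents state no rate. All trajectories are assumptions.

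| Scenario (E2, E4, E8, E12) | Mean of E2, E4, E8 | d = 0.10 | d = 0.23 | Bias |
|---|---|---|---|---|
| Building (−12, −12, −18, −20) | −14.0 | −19.4 | −18.6 | 0.6–1.4 toward null |
| Dose dip (−20, −12, −18, −20) | −16.7 | −19.7 | −19.2 | 0.3–0.8 toward null |
| Dip alone (−20, −12, −20, −20) | −17.3 | −19.7 | −19.4 | 0.3–0.6 toward null |
| Waning (−25, −20, −18, −15) | −21.0 | −15.6 | −16.4 | 0.6–1.4 away from null |

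Example: 0.77 × (−20) + 0.23 × (−14) = −15.40 − 3.22 = −18.62.

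**4. Cross-check from dose mismatch alone.** Shift in the pooled active mean = q × m × g, where:
- q is the share of the active arm imputed (5–22.9%, assumed);
- m is the share of those whose carried dose differs from the Week 4–12 dose;
- g is the LDL-C gap between doses (2–10 points, assumed, with less lowering on 60 mg).

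Protocol 1.2.2 expects about 25–30% of patients above target exposure at 100 mg. Using that as the 60 mg share is an assumption.
- All carried from Week 4: from 0.05 × 0.70 × 2 = 0.07 to 0.229 × 0.75 × 10 = 1.72 points toward null.
- All carried from Week 2: from 0.05 × 0.25 × 2 = 0.03 to 0.229 × 0.30 × 10 = 0.69 points away from null.
- Within the 100 mg group, all carried from Week 4: q × g, from 0.05 × 2 = 0.1 to 0.229 × 10 = 2.3 points.

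**5. Against sampling error.** SE at 70 versus 35 = 20 × √(1/70 + 1/35) = 4.14, so 1.4 points is 1.4/4.14 = 0.34 of one SE. The 1.72-point worst case takes the effect to 18.28. Pooled power at two-sided 0.05 (assumed, matching the SAP's 95% interval) then goes from 99.8% to 99.2%.

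**6. LOCF standard error.** A simulation with 70/35 patients, SD 20, visit correlation 0.5 and 10% or 23% dropout gave a sampling SD for the LOCF estimate of 4.09–4.20. The mean model SE was 4.13–4.16.

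**7. Gain from baseline.** Adjustment multiplies the SE by √(1 − r²): 0.995 at r = 0.1, 0.954 at r = 0.3 and 0.866 at r = 0.5. The documents do not give r.

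**The case against.** - **The dose gap may be small.** Planning assumes about −20% for any dose, and under that assumption bias from dose mismatch alone is zero. Dosing is guided by drug level toward one exposure range (Protocol 1.2.2), and Phase 1 showed significant LDL-C lowering from 50 to 200 mg (Protocol 1.1.1). This stands as a limit on size. It does not show that Weeks 2 and 4 equal Week 12, which LOCF also needs.
- **Not every carried value is at the wrong dose.** A reader might infer a general mismatch. The table in step 2 rules that out, and the SAP's primary contrast evaluates the titration regimen as a whole.
- **The upper bound is not a dose effect.** The 1.4-point figure comes from the building and waning scenarios, which are ordinary LOCF drift. This is correct; the dose dip gives 0.3–0.8.
- **Much is already covered.** Multiple imputation with baseline, an MMRM and a per-protocol repeat are planned. Early Termination visits collect lipids (Protocol 6.4.5, 6.6), which can supply a value at the current dose if it meets the two-day rule. This stands, but the headline estimate would still be the LOCF one.
- **MMRM is not assumption-free.** It relies on data being missing at random and, with treatment as its only group factor, does not settle by-dose classification. This stands, and is why LOCF and multiple imputation should remain.
- **The primary ANOVA is the larger departure.** It drops the baseline covariate that the protocol's ANCOVA requires, which matters more than the same omission from a sensitivity model. This stands; a baseline-adjusted primary MMRM would repair both.

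**Conclusion.** The point holds at modest size. LOCF is the primary method, a lone Week 2 or Week 4 value can become the Week 12 result, and the active arm's dose changes by protocol in between while placebo does not. Under the assumed trajectories and 10–23% imputed, the bias is about 0.3–1.4 points in either direction against a planned 20, and 0.3–0.8 toward the null in the dose-dip scenario. By-dose results are more exposed: up to 2.3 points in the 100 mg group if 22.9% are imputed, all from Week 4, with a 10-point gap. These figures illustrate scale only, because the documents give neither a dropout rate nor a dose gap.

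Two stronger readings are not supported. One is that pooled significance is at risk: worst-case power stays at 99.2%. The other is that LOCF understates its standard error: in simulation the model SE matched the estimate's sampling SD. The case for change rests on the estimate's accuracy and on a baseline covariate that the protocol requires and the planned MMRM omits.

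**What to change.** In SAP 3.7.2, make the primary analysis of percent change in LDL-C at Week 12 an MMRM with treatment, visit, treatment-by-visit, baseline LDL-C and baseline-by-visit terms, an unstructured covariance and the Week 12 contrast. Keep LOCF and multiple imputation as sensitivity analyses. Add baseline to the MMRM in 3.7.5. Because this model does not settle the by-dose question, also state how patients with no Week 4–12 dose are classed in the 3.7.3 final-dose repeat.

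At minimum, add baseline LDL-C to the MMRM already planned.

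The cost is SAP text: the model is planned, the data are collected and the sample size does not change. The downsides are reliance on missing at random for the primary result and a departure from the LOCF text of Protocol 10.2.1.1, which should be recorded with its reason before unblinding.
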